### **Primary Endpoint**

1. Daytime CO2 levels at the end of 4-6 weeks of therapy as determined by Arterial Blood Gas (PaCO2)

### **Secondary Endpoints:**

1. Average 30-day Ventilator Usage hours
2. Patient Comfort and Therapy Preference based questionnaire responses

### **Exploratory Endpoints:**

1. Other Ventilator Parameters
  - a. Respiratory Rate
  - b. Minute Ventilation
  - c. % flow limited breaths
  - d. Patient ventilation synchrony
2. Total therapy Titration Time
3. Screening session parameters
  - a. % flow limited breaths
  - b. Delta Xrs final screening value
4. Quality of Life Questionnaire
5. Activity (measured via the Actiwatch)
6. Reported Adverse Events
7. Sleep Quality
  - a. Total Sleep Time
  - b. Sleep Efficiency
  - c. Sleep Stage distribution
  - d. Arousal and awakening indices
  - e. Nocturnal TcO2 variability

[figure not shown]
- f. Nocturnal TcO2 averages
- g. Nocturnal SpO2 Saturation

## **V. Study Design:**

This will be a prospective, randomized, pilot study with cross-over design.

Patients who meet inclusion criteria will be randomized in a 1:1 ratio to receive either standard of care (SOC) NIV (control) or Vector (Active) for the first 4 to 6-week treatment period, followed by the other treatment during the second 4 to 6 weeks (see Figure 1). There will be two different patient cohort groups, patients that are current users of NIV and patients that are Naïve to NIV.

(Figure 1)

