### Secondary Objectives:

- To evaluate treatment effect of Vector on overall quality of life
- To evaluate treatment effect of Vector on sleep quality
- To evaluate treatment effect of Vector on physical activity levels
- To Evaluate treatment effect of Vector on Ventilator collected parameters
- To Evaluate treatment effect differences on nocturnal SpO2 and PaCO2 or TcCO2

**Endpoints:**Primary Endpoint:

Daytime CO2 levels at the end of 4-6 weeks of therapy as determined by Arterial Blood Gas (PaCO2)

Secondary Endpoints:

- Average daily device usage
- Therapy Comfort and Preference
- Incidence of Unanticipated Serious Adverse Device Effects (USADEs) and Serious Adverse Events (SAEs) for the Vector vs. the control group.

Exploratory Endpoints:

- Changes in quality of life scores ((CAT) SGRQ, dyspnea ratings mMRC),
- Ventilator collected parameter differences after 6 weeks of use (Respiratory Rate (RR), Minute Ventilation (MV))
- Sleep Quality differences as measured by PSG and actigraphy
- Changes in activity levels (mean and max activity counts)

**Study Population:** Approximately 30 COPD patients with chronic hypercapnia and evidence of expiratory flow limitation will be included.  
**Phase:** Pilot study

**Sites/Facilities Enrolling Participants:** Temple University Hospital

**Description of Study Intervention:** NIV with Auto Adjusting EPAP

**Study Duration:** Approximately 12 months

**Participant Duration:** Approximately 15 weeks

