### **Phone Follow-ups:**

Participants will be sent home with the Vector device with their randomized therapy. During the initial week, the participant will be contacted daily to determine if there are any problems with the device and to encourage compliance. Participants will be asked to use the Vector device at night for the following 6 weeks. Participants will then be contacted weekly from week 2 to the last week of their take home period (maximum of 6 weeks). During the second take home period, all participants will be called daily during the first week only.

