## **Study Visit 3 (Overnight Sleep Study) (within 4 to 6 weeks of visit 2)**

Participants will be asked to come to the sleep lab at a scheduled date and time. The sleep testing will begin near the subject's usual bedtime and ends at approximately 6 A.M.

Prior to the sleep study with the therapy device, the trained technologists will verify mask size, fit, and adjustment. The sleep test will involve using the device the participant has been receiving therapy from in the initial 4 to 6 weeks. Details of the PSG set up can be found in the standard procedures section of the protocol.

Morning ABG, Therapy Comfort and HRQL assessments: Following the completion of the sleep study (morning after), all participants will return to the research center where their activity monitors will be downloaded, fill out study-related questionnaires as well as have their ABGs collected. Details on ABG collection and study questionnaires can be found in the standard procedure section of the protocol. Participants in Cohort 1 that were randomized to their current NIV device for the initial 6 weeks will now be asked to use the Vector device for the next 6 weeks. The Vector device will be set up with the

Device settings determined during the titration procedure at study visit 2.

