## **Study Visit 4 (Overnight Sleep Study - within 4 to 6 weeks of visit 3)**

Participants will be asked to report to the sleep lab for the second overnight sleep study at a scheduled date and time. The sleep testing will begin near the subject's usual bedtime and end at approximately 6 A.M.

Prior to the sleep study with the therapy device, the trained technologists will verify mask size, fit, and adjustment that was determined at study visit 1. Details of the PSG set up can be found in the standard procedures section of the protocol.

Morning ABG, Therapy Comfort and QOL assessments: Following the completion of the sleep study (morning after), all participants will have to return to the research center where their activity monitors will be downloaded, fill out study related questionnaires as well as have their ABGs collected. Details on ABG collection and study questionnaires can be found in the standard procedures section of the protocol.

In the event that participants are unable to come into the research clinic for visit 3 or 4, remote administration of questionnaires via telephone or direct mail may be conducted. Participants may be asked to return their device SD cards via direct mail using a provided postage-paid envelope.

Procedures														
	Determine eligibility	Enrollment/Baseline		Visit 1 (day 0)		Visit 2 Daytime Titration		Week 1: Daily Check-in Calls		Weeks 2-6: Weekly Check-in Calls	Week 4: Diary Reminder Call 1	Visit 3 Overnight PSG study	Week 1: Daily Check-in Calls	Week 4: Diary Reminder Call 2
Chart Review	X													
Informed consent		X												
H&P , demographics		X												
QoL Questionnaires			X							X			X	
EFL assessment	X													
Morning ABG										X			X	
In Lab Sleep Study (PSG)										X			X	
Device titration (NIV Current)			X											
Device Titration (NIV Naïve)		X	X											
Clinical follow up (assess patients concerns/issues with device, mask, or other)										X	X		X	
Actigraphy set up/ data download		X								X			X	
Device data download (NIV Current)										X			X	
Device data download (NIV Naïve)				X										
Sleep Diary Reminder								X			X			
Side effects and AE assessment				X	X	X	X	X	X	X	X	X	X	

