### **Actigraphy Measurements & Sleep Diary**

Actigraphy is a method of measuring activity and sleep which is achieved by wearing a small watch-like device for an extended period of time. Most units contain an accelerometer and continually record the movement it undergoes. These data are later read to a computer for analysis. These data will provide an objective record of physical activity and sleep / wake patterns throughout the 6 weeks of home use.

The wrist-worn actigraph device will provide a continuous measure of both how much the participant has slept during the night and how active they are during the day. There is an event button that the participant will be asked to press when the participant is in bed, near asleep and also upon awaking.

Participants may be asked to keep a sleep diary during the last two weeks of each arm of the study in order to supplement the actiwatch data. The study team will call the participant to remind them to start using the diary.

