## **VIII. Assessment of Performance**

Device performance will be based on the following patient physiological and device recorded parameters:

- Daytime PaCO2 levels after 30-day period, method (Visits 3 and 4)
- Nocturnal TCO2 levels during sleep study (Visits 3 and 4)
- Nocturnal SpO2 levels during sleep study (Visits 3 and 4)
- Ventilator collected parameters over the 30-day use period (RR, MV, usage hours) (Visits 3 and 4)

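### Visits 3 and 4 are timed separately, so the two PaCO2 readings in a pair can follow exposures up to 14 days apart, and the sections disagree on period length

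*Combined protocol and SAP*

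**What the plan says.** Section V (Study Design) randomizes participants to SOC NIV or Vector "for the first 4 to 6-week treatment period, followed by the other treatment during the second 4 to 6 weeks". The primary endpoint is daytime CO2 "levels at the end of 4-6 weeks of therapy as determined by Arterial Blood Gas". The heading for Study Visit 3 places it "within 4 to 6 weeks of visit 2", and the heading for Study Visit 4 gives the same window counted from Visit 3. Neither section sets a target day, says how a date inside the window is picked, or links the second interval to the first.

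Other sections give different lengths:

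- Phone Follow-ups: "Participants will be asked to use the Vector device at night for the following 6 weeks", although the same paragraph treats 6 weeks as a maximum.
- Synopsis, exploratory endpoints: "Ventilator collected parameter differences after 6 weeks of use".
- Study Visit 3 (Cohort 1 crossover) and the actigraphy section also assume 6 weeks.
- Section VIII lists daytime PaCO2 "levels after 30-day period, method (Visits 3 and 4", and the first secondary endpoint in Section IV is a usage average over 30 days.

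On the diary, participants may be asked to "keep a sleep diary during the last two weeks of each arm of the study", while the schedule table fixes "Week 4: Diary Reminder Call 1" and puts a second reminder at week 4 of the second period.

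Section XI compares the therapies with a paired t-test or the Wilcoxon signed-rank test and rules out sensitivity analyses. It has no term for period, sequence or time on therapy.

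**The concern.** A crossover earns its precision by comparing each participant with himself or herself under like conditions. Here the time on therapy before the two blood gases can differ within a participant, and the analysis treats every pair as equivalent. If PaCO2 has not settled by week 4, part of a paired difference reflects exposure time and not therapy.

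The hypothesis in Section IV is that PaCO2 will be maintained at an equal level, so extra noise matters in a particular way: it makes a non-significant difference easier to obtain, and that could be misread as equality. The results may also be used to power a pivotal trial (Section XI) and to support regulatory clearance (Section XVII).

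The conflicting period lengths have practical effects too. They leave unclear when the primary endpoint is due, and they make one secondary endpoint and one data-collection step unworkable in the shortest permitted period.

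**Working it through.** The plan has no power calculation or stated figure to reproduce, so the check is arithmetic on the visit windows.

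**Exposure gap**

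- Shortest period: 4 × 7 = 28 days. Longest: 6 × 7 = 42 days (Section V; Visit 3 and Visit 4 headings).
- Largest gap within a pair: 42 − 28 = 14 days. Largest ratio: 42/28 = 1.5.

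**A less extreme picture (assumption).** The documents do not say how dates fall in the window. Suppose the two lengths are independent and uniform over the 15 whole days from 28 to 42.

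- Mean absolute gap: (15² − 1)/(3 × 15) = 224/45 = 5.0 days.
- Share of pairs at least 7 days apart: 2 × (8 + 7 + … + 1)/15² = 72/225 = 32%.

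**What a gap could do to PaCO2 (assumption).** The documents give no time course. Suppose PaCO2 falls linearly by s mmHg between weeks 4 and 6, with s anywhere from 0 to 1. A gap of d days then shifts that pair by s × d/14:

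- d = 14: 0 to 1 mmHg.
- d = 5: 0 to 5/14 = 0.36 mmHg.

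If the gap is unrelated to therapy, these shifts average to zero across participants and only add spread. They move the mean contrast only if one therapy tends to get the longer period.

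**30-day usage.** 28 < 30, so a 28-day period is 2 days short of the averaging window.

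**Diary.** Week 4 is days 22 to 28. A diary of the last 14 days starts at day L − 14 of an L-day period.

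- L = 42: it starts at day 28, so the week-4 call is on time.
- L = 28: it starts at day 14, so the call comes 8 to 14 days late, leaving 28 − 22 = 6 days at most and none at worst.

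**Cohort 2, SOC first.** The Randomization section keeps these participants on the SOC settings used during the 2-week acclimation. Before the first blood gas they therefore have 28 + 14 = 42 to 42 + 14 = 56 days on SOC (before the +2-day visit allowance), against 28 to 42 on Vector. The ratio runs from 42/42 = 1.0 to 56/28 = 2.0.

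**The case against.** The strongest reply is that this is a flexible visit window in a small pilot with no power claim, and that the text leans towards 6 weeks. Participants are asked for 6 weeks of use, check-in calls run to week 6, and the stated participant duration of about 15 weeks fits two full periods: (9 + 84)/7 = 13.3 weeks at most for Cohort 1 and (16 + 84)/7 = 14.3 for Cohort 2. On that reading 4 weeks is an early limit and most pairs would be close. Order is randomized 1:1, so a habit such as a later second visit is balanced across therapies in expectation. Day 30 lies inside the window, so some of the conflicting wording is loose drafting. Time on therapy should be recoverable from visit dates and device downloads.

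Most of this stands, and it limits the point. It does not remove it: the endpoint and both visit headings permit any length from 28 to 42 days, and nothing asks for the two to match.

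A reader might infer three stronger things that the documents do not support:

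- **That 50% more exposure on one therapy is typical.** It is the corner of the window.
- **That the contrast is biased because visits are moved according to how a therapy is tolerated.** The text says only that visits are scheduled. No masking is described in the text available (Figure 1 is not shown), so such scheduling is possible, but nothing shows it.
- **That the diary is lost altogether in a 4-week period.** A call early in week 4 would save about 6 days. The diary is also optional and only supplements actigraphy.

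**Conclusion.** The point holds as a design weakness of moderate size. Exposure before the paired PaCO2 readings can differ by up to 14 days, and the planned analysis neither prevents nor accounts for this. The consequence is avoidable within-pair variation, provided PaCO2 is still changing after week 4. If it has settled by then, the effect on the primary endpoint is nil. Any figure in mmHg rests on an assumed drift. Bias would additionally need visit timing that depends on therapy.

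The inconsistencies need no such assumption. The documents give period length as 4–6 weeks, 6 weeks and 30 days. A 28-day period cannot yield a 30-day average, and a week-4 reminder cannot serve a last-two-weeks diary in a period that ends at week 4.

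**What to change.** 1. Keep the sponsor's 4–6-week range, but schedule Visit 4 the same number of days after Visit 3 as Visit 3 fell after Visit 2, within about ±3 days and not beyond 42. The largest gap then falls from 14 days to about 3.
2. Report days on therapy at each blood gas, so that any remaining imbalance is visible by therapy and by sequence.
3. Place the diary reminder 14 days before the booked Visit 3 or Visit 4 instead of at a fixed week 4.
4. Reconcile the period lengths in the Synopsis, the primary and secondary endpoints in Section IV, Phone Follow-ups, Study Visit 3, the actigraphy section and Section VIII. Define a usage-averaging window that every permitted period can supply.

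The cost is protocol wording and a scheduling rule. The second visit becomes less flexible around sleep-lab booking, repeat sleep studies and exacerbations, so some window deviations should be expected. Two matters are left open: matching the visits does not remove the extra two weeks on SOC settings for Cohort 2 participants randomized to SOC first, and it does not address the absence of a washout.

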### A. Schedule of Events:

#### Screening Procedures:

##### Study Participation Screening (Prior to Visit 1)

Participants will be contacted by designated study staff from Temple University Lung Center Research Team. Participants may be pre-screened through medical records over the phone to determine eligibility. A screening script will include a general review of key inclusion and exclusion criteria. Participants that are interested will be scheduled for the screening visit at the clinical office.

Upon screening, study participants will be divided into 2 different cohorts – current NIV users and participants that are Naïve to NIV therapy.

## *COVID-19 Screening Procedure (All visits)*

Due to the COVID-19 pandemic, participants may be screened for COVID-19 symptoms over the phone prior to each scheduled study visit. During each study visit, participants may be asked to complete a self-declaration form, which asks about COVID-19 exposure, current symptoms, and confirms that participants have been briefed on safety measures. The form will be used for safety purposes and is not intended for data collection. Site COVID-19 safety procedures and documentation will also be followed. Study products and materials will either be single use or will be cleaned and disinfected per the multi-patient use guidelines in the Instructions for Use.

### **Study Visit 1 (screening)**

Once the participants arrive, the study will be explained in full detail. If the participant agrees, he/she will be consented into the study and the participant will be given a copy of the informed consent.

Once consent is obtained, and eligibility is confirmed, the following study related procedures will be conducted:

- Demographics: sex, age, ethnicity, and race will be collected
- Anthropometric Measurements: height, weight, neck circumference will be collected.
- Current Medications: all current medications will be collected.
- Medical History Assessment: information will be collected regarding historical spirometry data, PaCO2 level at the time of NIV initiation, COPD history questionnaire, smoking history and other relevant medical history including the diagnosis of Sleep disordered breathing.
- Physical examination with vital signs to include HR, BP, RR, and SPO2 maintained at least 88%, and chest auscultation.
- Administration of CAT and STOP-BANG questionnaires.
- Urine pregnancy test for women of childbearing potential
- Mask Fitting: Participants may have up to two mask fittings in order to determine the best possible provided mask while using the Vector NIV device.

## EFL Screening/Determination and EPAP Titration

- For the EFL Screening/Determination and EPAP Titration procedure, the following device settings will be applied:

• Pressure Support	6 cmH 2 O
• Max Pressure	26 cmH 2 O
• EPAP Min / EPAP Max	4 / 20 cmH 2 O
• EPAP setting	Auto
- EFL Determination: The participant will be asked to lie supine or semi-recumbently while breathing into the Vector NIV device using the selected mask initially for 5 minutes. This device has a screening test that has the capability of detecting and estimating the severity of EFL. If it is determined that the participant does not have EFL after 5 minutes by the device screening indicator, the participant will not continue in the study. After the screening is complete, participants will be asked a couple of questions about their experience.
- EPAP Titration: If it is determined by the Vector NIV device that the participant has EFL, the Vector NIV device will be changed from screening mode to therapy mode to delivery BiPAP therapy. The participants will then breathe on the Vector NIV device in the supine position for an additional 20 minutes approximately. During the additional 20 minutes of breathing, the device will automatically increase the EPAP (and concurrently and proportionally the IPAP) until the EFL is abolished (falls below the predetermined EFL threshold). After the titration is complete, participants will be asked a few questions about their experience
- While the automatic EPAP Titration is being performed all participants' SpO2 will be monitored via finger pulse oximetry. Oxygen will be provided to patients at the clinician's discretion.
- Patient must stay awake during the EPAP Titration. If the patient falls asleep, they will be awoken by study staff.
- The Final EPAP that is determined to abolish the participants EFL will be recorded. If the determined EPAP pressure is 6cmH2O or higher, the participant may continue to study visit 2. If the determined EPAP is below 6cmH2O then the participant will not be scheduled for study visit 2.
- Participants that are determined to have EFL and a titrated EPAP  $\geq$  6cmH2O will be eligible to continue in the study.

- Current NIV users who also have a clinical diagnosis of OSA must have a calculated final titrated EFL EPAP that is higher than their EPAP settings of their current NIV device in order to continue in the study and to be scheduled for study visit 2.

### **NIV SOC Titration (NIV Naïve Cohort only)**

Participants who are NIV naïve and determined to have EFL with a titrated EPAP >6cmH2O will then undergo standard SOC titration (Appendix A) in order complete a 2 week NIV acclimation period. Initiation of SOC titration will take place under the supervision of the study investigator, research coordinator and / or healthcare professional (Respiratory Therapist, Sleep Technician, etc.).

After successful completion of the device titration, participants will be given one-on-one operational instructions on the Vector device by clinical study staff. The Vector therapy will not be enabled. The device will be set up with the optimal pressures determined from the SOC titration. In addition to the application of the settings determined by the SOC titration, the Automated Airway Management (AAM) feature will be enabled with the minimum set EPAP to 4 cmH2O and a maximum of 20 cmH2O. This feature will adjust the EPAP to maintain upper airway patency.

The purpose of the 2 week NIV acclimation period is to determine if the patients that are naïve to NIV will adhere to therapy and also if they potentially have underlying OSA that require 90% EPAP pressures higher than the determined EFL titrated EPAP at the screening visit. After receiving training on the device, participants will also be given a user manual, mask, and tubing and be asked to use the device at home for 2 weeks.

### **Study Visit 2 (Randomization and Titration)**

Upon successful completion of the screening procedures, participants in the NIV current user cohort will be asked to return to the research center within the next 7 days (+2 days). Study participants in the NIV naïve Cohort will be asked to return to the research center in 14 days (+ 2 days). Participants in the NIV naïve cohort will have the data from their device downloaded and reviewed.

Participants in the NIV naïve cohort will be excluded from continuing in the study if the average nightly device use is < 4 hours per night **OR** the average nightly 90% EPAP pressures are greater than the titrated EFL EPAP pressure determined during the screening visit. 90% EPAP values will be accessed through the CareOrchestrator patient management platform.

During study visit 2, qualified participants will be randomized to one of the two therapy orders. In addition to being randomized, participants will be set up with the activity

monitor, fill out baseline study questionnaires, receive one-on-one training and instructions on how to use the Vector device.

